PCP recruitment has been completed for this study as of February 10, 2017. No further PCP enrollment or study sessions will take place after this date.

The study aims to enroll 50-120 PCPs as participants. PCPs will be recruited through print/flyer advertisements in department offices and health centers, email invitations, announcements at departmental meetings, and a presentation at CHA medical grand rounds and family medicine grand rounds. The presentation for Medicine grand rounds will take place on October 1st, 2014, and the presentation for Family Medicine grand rounds will take place on September 30th, 2014. The study aims to enroll at least 25-40 PCPs into an intervention group (Group 1) and at least 25-40 into a control group (Group 2 and 3).

C.2.b. Patient Recruitment:

The study aims to enroll a total of 434-1,000 CHA patients as participants during the project. Patients will be recruited through print/flyer advertisements in health centers, CHA marketing materials, community informational meetings, and referral by PCPs and other members of the health care team. In addition, we aim to develop a video introduction about mindfulness to be played in patient waiting areas within health centers with translations into the primary languages of the health centers (Once developed these videos will be provided for review by the CHA IRB prior to implementation). This study aims to randomize 290 patients to an 8-week study intervention and another 144 to a control group.

C.2.c. Experimental fMRI Pilot Patient Recruitment:

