Within this naturalistic implementation project, we will conduct a randomized controlled trial of CHA patients with a PCP referral. Patients will be randomized using a stratification algorithm to receive either MTPC training or one 60-min introduction to mindfulness session. This randomization will be based on the level of mindfulness training of the patient’s primary care provider (Group 1 vs. Group 2 and 3). Those patients who are randomized to receive MTPC training (MTPC Group) will be instructed by behavioral health specialists who are trained as MTPC Group Leaders, as described later in section C.4.a. of the protocol. The MTPC group is a group psychotherapy intervention held within a primary care health center on 8 consecutive weeks with 10-12 enrolled patients with 2 hour-long sessions, including a 7-hr day of silent practice. As the level of desire to participate in mindfulness training may be a confounding factor, we will use a 60-min introduction to mindfulness group as a control in order to eliminate bias related to expectation and selection that could otherwise influence measures of treatment effect. In contrast, those patients who are randomized to receive only the 60-min introduction to mindfulness (Control Group) will be given preference to enroll in MTPC after the study’s completion. Both groups of patients will complete surveys at the induction of the study, again after patient study week 8, and at study week 26 (see Figure 1b). Patients will complete an interview with a research coordinator to assess their maintenance of their action plan goal at week 26.

Figure 1b. Study flow schema for Patient participants

In this RCT, we will also conduct an optional experimental fMRI pilot study. This study will include a pre/post within-subjects design with 90 minutes of neuroimaging before and after completion of the MTPC group. Each scanning session will begin with setting up the equipment for autonomic monitoring (i.e., respiratory belts, finger plethysmograph, finger sensors for skin

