All patient participants will receive an ongoing 3-5 minute Participant Engagement phone call from a member of the study staff. This call will be made according to the brief phone script attached. This call will be made every two weeks during Study Weeks 1-8. The purpose of this outreach call will be to provide support for patients in both groups, help participants cultivate a relationship with study staff, give participants a place to ask questions, and support participants in completing study visits. The call will have five talking points: 1) How have you been in the last 2 weeks? 2) Have you had any issues with completing the weekly Mindfulness Practice Diary or the Mindfulness Resources Use Diary? 3) Have there been any issues with your participation in the study in general? 4) We appreciate your contribution to the research study and encourage you to continue filling out the diaries – just as a reminder you will receive \$20 for each survey session and \$20 if you complete all the weekly diaries. 5) Is there anything else you'd like to share with us? Study staff will complete a call log for all engagement calls, and issues raised in these calls will be discussed twice a week in research staff meetings.

Mindfulness Intervention (MTPC Intervention Group; PT Study Week 1-8):

Patients in the 8-week MTPC program will meet with a behavioral care provider for 8 weeks in groups of approximately 6-12 participants, to receive 2 hours of instruction in MTPC. MTPC groups will be generally held in the evenings in clinical spaces within each participating CHA primary care health center. Between weeks 6 and 7 there will be a weekend 7 hour long day of silent practice at locations within the local community or within a nearby CHA hospital facility space. The total duration of the program is 23 hours over 8 weeks with additional expectations

for daily home practice by participants. Details about this intervention can be found in section C.3.e.4.

Action Plan Study Session (Completed between PT Study Weeks 6-7):

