Post-treatment Survey Session Computer Visit 2 (Completed at PT Study Week 9):

In this session, patient participants will complete the Action Plan Initiation Survey (APIS-5). This survey is expected to take approximately 5 minutes to complete.

Post-treatment Survey Session Computer Visit 3 (Completed at PT Study Week 10):

In this session, patient participants will complete the Action Plan Initiation Survey (APIS-5). This survey is expected to take approximately 5 minutes to complete.

Post-treatment Survey Session Computer Visit 2 (Completed at PT Study Week 16):

In this session, patient participants will complete the Action Plan Initiation Survey (APIS-5). This survey is expected to take approximately 5 minutes to complete.

Follow-up Survey Session Computer Visit (Completed between PT Study Weeks 24-26):

After six months, both patient groups will complete a survey about attitudes about primary care providers. Patient participants will again be given the option to either visit their PCMH to complete the surveys on a CHA device, on paper, or complete the surveys outside of the office on a computer of their choosing. Patients requiring interpreters or electronic devices can schedule a meeting visit at their PCMH to complete the surveys. These surveys are expected to take the average patient 70 minutes to complete.

In this session, patient participants will complete the Patient Mindfulness Self-Report Battery, the Patient Clinical Assessment Battery, the Patient Self-Management Battery, the Patient-PCP Relationship Battery, the Action Plan Initiation Survey (APIS-5), the Weekly Mindfulness Practice and Resources Diaries, and the Adverse Event Reporting Form.

Waitlist patient participants must complete the following study requirements in order to be eligible for a spot in the next MTPC group once their 6-month study participation has ended: three 45-minute study survey batteries, the Action Plan Worksheet, 1 of 3 Action Plan Follow-Up Surveys, and 6 of 8 weekly Mindfulness Practice/Resource surveys.

Action Plan Interview (Completed after PT Study Week 26): After completing the study, participants will have an opportunity to give comments about their experience in the MINDFUL-PC program.

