Using an intent-to-treat analysis with 290 patients receiving mindfulness training and 144 patients with orientation only, there will be an 80% chance of detecting a significant difference at a two-sided 0.05 significance level. This assumes that the rate of action plan initiation is 0.54 in orientation only (based on Guck et. al. [70]) and the rate of action plan initiation among patients who receive mindfulness training is 0.68 (based on rates of initiation and maintenance of meditation practice in previous pilot MBIs [94]). After the first twenty participants complete the program, an interim analysis of these pilot data may be used to refine the sample size calculation for RCT.

D. Human Subjects Procedures and Confidentiality

D.1. Confidentiality:

D.1.a. Protection of Subject Privacy:

All of the materials collected are for research purposes only, and data will be kept in strict confidence. No information will be given to anyone without permission from the subject. Confidentiality will be ensured by use of identification codes. All data will be identified with a unique numeric identification code and an acrostic that are unique to the subject. Any data collected before a participant discontinues the study is available for use in this research project.

All research session data will be collected using standardized electronic forms on designed using the REDCap database hosted by Cambridge Health Alliance. REDCap (Research Electronic Data Capture) is a secure, web-based application designed to support data capture for research studies, providing an intuitive interface for validated data entry and export procedures to common statistical packages. All data management will be conducted by the research team operating

from CHA. All data collection will take place under the supervision of the [name] and the Data Manager. Data will only be collected by members of the research team.

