D.4.b.1. Measurement and Reporting of Subject Accrual, Compliance With Inclusion/Exclusion Criteria:

Review of the rate of subject accrual and compliance with inclusion/exclusion criteria will occur monthly by the data manager with reports to PI every 3 months to ensure that a sufficient number of participants are being enrolled and that they meet eligibility criteria and the targeted ethnic diversity goals outlined in the grant proposal (Targeted/Planned Enrollment Table).

D.4.b.2. Measurement and Reporting of Participant Adherence to Treatment Protocol:

Data on adherence to the treatment protocol will be collected twice weekly by research staff and reviewed quarterly by the PI, the study statistician, and the independent monitor. Adherence of patient participants will be evaluated by attendance at MTPC groups, PCP visit, and completion of all study sessions. Adherence for each session will be rated on the following scale: 0 = absence; 1 = completed; 2 = incomplete (with comments). An explanation of study staff attempts to understand and address participant adherence deficits will be documented and reviewed twice weekly.

D.4.c. Justification of Sample Size:

The goal of the study is to determine if Mindfulness Training provided in Primary Care results in a greater decreases in anxiety, stress, and depression than referral to community resources. The study is also powered to assess for effects of mindfulness training on provider-patient relationship. The current RCT is funded by AVDF and Gold Foundation and is sufficiently powered to address these aims.

Using an intent-to-treat analysis with 290 patients receiving mindfulness training and 144 patients with orientation only, there will be an 80% chance of detecting a significant difference at a two-sided 0.05 significance level. This assumes that the rate of action plan initiation is 0.54 in orientation only (based on Guck et. al.[5]) and the rate of action plan initiation among patients who receive mindfulness training is 0.68 (based on rates of initiation and maintenance of meditation practice in previous pilot MBIs[6]).

The experimental fMRI pilot trial will recruit primary care patients (n= max. 30 subjects) with anxiety or depression from the MTPC arm using a within-subject pre/post design, which is an adequate size for a pilot neuroimaging trial to be able to assess an effect size of the fMRI and medical regimen adherence measures needed to power the trial for the UH3 phase.

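### The stated 80% power holds only for independent, complete outcomes at 290/144; nothing is allowed for therapy-group clustering in the MTPC arm or for missing initiation data, and no cluster term is named for the binary endpoint

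*Combined protocol and SAP*

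**What the plan says.** C.5.c gives one power statement for the MTPC comparison: with "290 patients receiving mindfulness training and 144 patients with orientation only, there will be an 80% chance of detecting a significant difference". D.4.c repeats it: "there will be an 80% chance of detecting a significant difference at a two-sided 0.05 significance level". The inputs are action plan initiation rates of 0.54 (orientation only) and 0.68 (MTPC) in 290 and 144 patients, analysed by intent to treat. Neither section mentions an ICC, a design effect, an attrition rate or an inflation factor.

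The recruitment target uses the same numbers. C.2.b says "This study aims to randomize 290 patients to an 8-week study intervention and another 144 to a control group", D.3.b.2 agrees, and Table 1 splits them as 145 + 145 and 72 + 72. C.2.b also gives an enrolment range: "The study aims to enroll a total of 434-1,000 CHA patients as participants during the project". C.5.c adds that after the first twenty completers "an interim analysis of these pilot data may be used to refine the sample size calculation for RCT".

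MTPC is a group treatment. C.3.a says "The MTPC group is a group psychotherapy intervention held within a primary care health center on 8 consecutive weeks with 10-12 enrolled patients"; C.3.d.2 says that patients "meet with a behavioral care provider for 8 weeks in groups of approximately 6-12 participants". C.3.h lists loss to follow-up as a reason for discontinuation.

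For binary initiation, C.5.b item 5 names logistic regression and mixed effects modelling. It names no random effect, cluster level, defining visit or missing-data rule. C.3.d.2 and Table 3 schedule APIS-5 at the post-treatment session, weeks 9, 10 and 16, and the follow-up session in weeks 24-26. The description of the instrument in C.3.f.6 gives weeks 8, 12 and 16.

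**The concern.** The power calculation treats all 434 patients as independent and fully observed, and the plan gives reason to doubt both. Patients in the same MTPC group share a leader, a room and each other for eight weeks, so their outcomes may be correlated, and this happens in one arm only. The action plan is written in weeks 6-7, after randomisation, so a patient who leaves early may have no goal and no initiation outcome.

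Because the number powered for is also the number to be randomised, neither feature has been absorbed elsewhere. At stake is whether a reader can see what power the trial has. There is also a question of validity: if binary initiation is tested by ordinary logistic regression while outcomes within groups are correlated, the MTPC test rejects too often under the null. A larger sample does not cure that.

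**Working it through.** **Inputs from the documents.** p_C = 0.54, p_M = 0.68, n_C = 144, n_M = 290, two-sided alpha 0.05 (C.5.c); group size m from 6 to 12 (C.3.a, C.3.d.2). **Assumed, because the documents give none:** the ICC and the loss rate.

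**1. Reproduce the stated figure.** Pooled proportion = (144 × 0.54 + 290 × 0.68)/434 = 0.6335.
- SE under the null = √[0.6335 × 0.3665 × (1/144 + 1/290)] = 0.04912.
- SE under the alternative = √[0.54 × 0.46/144 + 0.68 × 0.32/290] = 0.04975.
- Power = Φ[(0.14 − 1.96 × 0.04912)/0.04975] = 81.0%. With the unpooled SE throughout, 80.3%.

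The same formula at 2:1 needs 141 + 282 = 423 patients for 80%, so the reserve is 434 − 423 = 11 patients, or about 1 point of power.

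**2. Clustering in the MTPC arm only.** Replace n_M by 290/[1 + (m − 1) × ICC] and leave n_C at 144. The number of groups runs from 290/12 ≈ 24 to 290/6 ≈ 48.

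| ICC | Power, m = 6 | Power, m = 12 |
|---|---|---|
| 0.01 | 80.4% | 79.6% |
| 0.02 | 79.7% | 78.1% |
| 0.05 | 77.7% | 73.9% |

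For example, at ICC 0.05 and m = 12 the design effect is 1.55, and 290/1.55 = 187 effective patients. Power crosses 80% at an ICC of about 0.016 (m = 6) or 0.007 (m = 12).

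**3. Missing outcomes, no clustering.** The answer depends on a rule that the plan does not state.
- Complete case: multiply both arms by (1 − loss).
- Missing counted as not initiated: keep 290/144 and multiply both rates by (1 − loss). At 10% loss the rates become 0.486 and 0.612.

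| Loss, equal in both arms | Complete case | Missing = not initiated |
|---|---|---|
| 10% | 76.9% | 70.4% |
| 20% | 72.0% | 59.5% |

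Complete-case power crosses 80% at about 2.6% loss. Loss here means no usable value for the endpoint. If any of the scheduled APIS-5 sessions can supply it, missing one session does not lose the patient.

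**4. The enrolment ceiling.** With 1,000 randomised 2:1, ICC 0.05 and 20% complete-case loss, power is 94.3% (m = 12) to 95.9% (m = 6).

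**5. Level of an unclustered test.** With D = 1 + (m − 1) × ICC, actual level = 2 × {1 − Φ[1.96 × √((1/290 + 1/144)/(D/290 + 1/144))]}.

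| ICC | Level, m = 6 | Level, m = 12 |
|---|---|---|
| 0.01 | 5.2% | 5.4% |
| 0.02 | 5.4% | 5.8% |
| 0.05 | 6.0% | 7.1% |

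**The case against.** The strongest reply is that nothing stated is wrong. The 80% is correct on its inputs, and every shortfall above comes from an ICC or a loss rate that the documents do not contain. At ICC 0.01-0.02 with full data, power still rounds to about 80%. That stands, and it limits the point to an unstated assumption.

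The plan also has room and safeguards. Enrolment may reach 1,000, which would more than restore power. Both arms receive biweekly engagement calls (C.3.d.2). The extra APIS-5 sessions are paid and there is a completion bonus (D.7). Patients terminated from MTPC groups are still expected to complete assessments (C.3.h), and waitlist patients must complete specified surveys to qualify for a later group (C.3.d.2). These may well limit loss. But no section presents any of them as an allowance, the enrolment range is not explained, the look after twenty completers is optional and names neither clustering nor loss, and the power statement stays at 290/144.

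On the analysis, a mixed logistic model with a group effect falls within the wording of C.5.b item 5. A reader might infer that the plan commits to an invalid unclustered test. It does not: such a test is permitted, not required.

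A reader might also infer that the trial is underpowered. The documents do not support that either, since the true ICC and loss are unknown and more than 434 patients may be enrolled.

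**Conclusion.** The point stands as an omission, with confidence high on the omission and low on its size. The 80% applies to 434 independent, complete outcomes and has about 1 point in reserve. Small departures take it below 80%, although the fall is slight at small ICCs and substantial only at ICC 0.05 or with loss of 10% or more. Missing data could matter more than clustering, and its effect depends heavily on the unstated rule: at 20% loss the two rules differ by 72.0 − 59.5 = 12.5 points. Inflation of the type I error is conditional on both an unclustered logistic analysis and correlation within groups; at ICC 0.01-0.02 it is less than 1 point. All figures assume equal group sizes, equal loss in both arms and no correlation in the control arm. This should be fixed, but it does not show the stated calculation to be mistaken.

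**What to change.** 1. In C.5.c and D.4.c, state that 80% assumes independent, complete outcomes at 290/144. Give power over a declared range of ICC (including 0.01-0.05), group size (6-12) and loss, under the missing-outcome rule that will be used. Give the range and not a single worst-case figure. If enrolment above 434 is meant as the allowance, say so.

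2. In C.5.b item 5, state one analysis of binary initiation. It should account for MTPC group in the MTPC arm, by a group random intercept in that arm or a cluster-robust variance, and include the randomisation strata (health center, PCP group). It should also name the APIS-5 visit or visits that define initiation, with C.3.f.6 brought into line with C.3.d.2 and Table 3, and say how missing outcomes are handled.

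The cost is protocol wording and a different model specification in SAS; the changes themselves need no new patients or data. The downside is a less favourable stated power and slightly wider intervals.

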An adverse event (AE) is any untoward medical occurrence in a subject during participation in the clinical study. An adverse finding can include a sign, symptom, abnormal assessment (from vital signs or brain imaging), or any combination of these.

A serious adverse event (SAE) is any AE that results in one or more of the following outcomes:

Death

A life-threatening event

Inpatient hospitalization

A persistent or significant disability/incapacity

A congenital anomaly or birth defect

An important medical event based upon appropriate medical judgment.

D.2.b. Classification of AE Severity:

AEs will be labeled according to severity, which is based on their impact on the patient. An AE will be termed “mild” if it does not have a major impact on the patient, “moderate” if it causes the patient some minor inconvenience, and “severe” if it causes a substantial disruption to the patient’s well-being. Of note, a severe AE and a serious adverse event (SAE) are distinct terms. A subject could experience a severe AE that does not meet the above-listed definition of an SAE; alternatively, a subject could experience a moderate AE that meets the SAE definition.

D.2.c. AE Attribution Scale:

AEs will be categorized according to the likelihood that they are related to the study intervention. Specifically, they will be labeled definitely unrelated, probably related, possibly related, or definitely related to the study intervention.

D.2.c.1. AE Reporting and Follow-up:

This study will comply with the reporting requirements from the Cambridge Health Alliance IRB. The PI will report to the IRB, Independent Monitor, and NCCIH any of the following *unanticipated problems* and *adverse events* that occur 1) during the conduct of the study, 2) after study completion, or 3) after subject withdrawal or completion:

1. *Internal adverse events* that are *unexpected*, and related or *possibly related to the research* and that indicate there are new or increased risks to subjects;
2. *External adverse events* that are *serious*, *unexpected*, and related or *possibly related to the research* and that indicate there are new or increased risks to subjects that require some action (e.g., modification of the protocol, consent process, or informing subjects);
3. *Deviation* from the approved research protocol or plan without IRB approval in order to eliminate apparent immediate hazard to subjects or harm to others;

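### In D.2.b the mild and moderate adverse-event grades overlap and can invert; secondarily, D.2.c has no label for an event that is unlikely, but not certain, to be unrelated

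*Combined protocol and SAP*

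**What the plan says.** Section D.2.b puts severity on a single scale: "AEs will be labeled according to severity, which is based on their impact on the patient". The three grades are then defined as follows.

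- *Mild*: "if it does not have a major impact on the patient".
- *Moderate*: "it causes the patient some minor inconvenience".
- *Severe*: "if it causes a substantial disruption to the patient’s well-being".

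The same paragraph separates severity from seriousness. It notes that a moderate event may meet the SAE definition and that a severe one may not.

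Section D.2.c sets the attribution labels: "definitely unrelated, probably related, possibly related, or definitely related to the study intervention".

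The scales are applied in more than one place. Under D.2.c.2 the investigator or other study staff log AEs at baseline, at any fMRI session, weekly during the intervention, at the post-study and follow-up sessions, and ad hoc. Under C.3.f.13 a participant self-report form at 8 weeks and 6 months asks for the parameters set out in D.2. Section D.4.f calls for an annual report that lists and summarises AEs.

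The protocol gives no cut-points, worked examples, tie-break rule or grading dictionary. The opening of D.2 says that the AE guidelines are copied from the DSMP, whose text is not in the document reviewed.

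**The concern.** A severity scale should place each event in exactly one grade, with worse events never graded lower. The first two grades here fail on both counts. *Mild* is defined only by an upper limit (not major), while *moderate* is defined by something small (a minor inconvenience) that lies well inside that limit. Two raters who follow the text faithfully can grade the same event differently, and several kinds of rater use the scale, including participants themselves.

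The attribution scale has a related weakness. A rater who thinks an event is unlikely to be due to the intervention, but cannot exclude it, finds no matching label.

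What is at stake is the quality of the safety description: the mild/moderate breakdown and the related/unrelated breakdown in the AE log and in the reports drawn from it. The efficacy analyses in C.5.b do not use either scale.

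**Working it through.** This is a question of definitions, so the check is by enumeration. The plan states no figure on this point to reproduce.

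**Severity.** The inputs are the three definitions in D.2.b. Take four ordered levels of impact and ask which definitions each one satisfies, reading *major* in the mild definition and *substantial* in the severe definition as the same threshold.

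| Impact on the patient | Mild (not major)? | Moderate (minor inconvenience)? | Severe (substantial)? | Grade under the text |
|---|---|---|---|---|
| 1. None | yes | no | no | mild |
| 2. Minor inconvenience | yes | yes | no | mild or moderate |
| 3. More than minor, less than major | yes | no | no | mild |
| 4. Major or substantial | no | no | yes | severe |

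Two results follow.

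- *Overlap.* Row 2 satisfies two grades. A minor inconvenience is by its nature not a major impact, so every event that qualifies as *moderate* also qualifies as *mild*. No event is moderate only.
- *Inversion.* Row 3 is worse than row 2 but can only be *mild*, while row 2 may be called *moderate*.

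The paragraph itself suggests that the wording misses its purpose. It allows a moderate event to be an SAE, and the SAE list in D.2.a includes inpatient hospitalization. That sits awkwardly with a grade defined by minor inconvenience.

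**Attribution.** The input is the list in D.2.c: four labels, one unrelated and three related. Having only one unrelated label is not an error in itself. The difficulty is that this label requires certainty and the next one down in likelihood is *possibly related*. An event with any residual doubt fails *definitely unrelated*, and the lowest label left is *possibly related*. The displacement is therefore mainly in one direction, into the related class. If a share *u* of all events is judged unlikely but not certain to be unrelated, the related share rises by up to *u*. The documents give no AE rates and nothing from which to estimate *u*, so any number put on this would only restate its own assumption.

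**Where the labels are used.**

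- D.2.c.1 makes internal AEs reportable on unexpectedness, relatedness (including possible relatedness) and new or increased risk. The severity grade is not a criterion.
- D.2.c.3 asks the investigator to explain why an event is unexpected, and severity is one permitted ground. The link is through a narrative judgement; the D.2.b grade is not named as the test.
- D.2.c.5 uses possible relatedness in its general SAE rule, relatedness without that qualifier in the 7-day and 15-day rules, and a less urgent route for anticipated or unrelated SAEs. The section does not say whether *possibly related* counts as related for the 7-day and 15-day rules.
- The stopping rules in D.4.d cite no grade. The reports in D.4.f and D.4.g specify no table by grade or by relatedness.

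**The case against.** The strongest reply is that very little depends on the flaw. SAE status is set by outcome. The reporting triggers do not use the severity grade, the stopping rules do not mention it, and C.5.b contains no AE analysis. The Independent Monitor reviews AE and SAE reports, and unrelated SAEs are still reported, so a wrong mild or moderate label does not hide an event. On attribution, over-counting related events is the cautious direction for safety reporting, and a coarse scale is partly a design preference. The DSMP, the AE log and the self-report form might also contain cut-points that settle the matter.

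Most of this stands, and it limits the point to the quality of safety description. It does not remove the point: the protocol states a grading rule, that rule gives two answers for one class of event and a reversed order for another, and nothing in the document resolves it. If the unseen forms do carry clearer definitions, they differ from the protocol and the two need aligning.

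Three stronger readings are tempting and are not supported.

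- A reader might infer that graded and related AE counts as a whole are unusable. The overlap touches only mild versus moderate.
- A reader might infer that the missing attribution level could push the related count either way. The word *definitely* in the only unrelated label makes the shift mainly upward.
- A reader might infer bias between arms, because C.3.c says the study is not blinded. Open assignment does leave room for that, but D.4.g makes the routine report tables aggregate, confines group-level safety data to a masked closed report for the Independent Monitor, and no comparison of grades between arms is planned.

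**Conclusion.** The point holds in a limited form. The mild and moderate definitions in D.2.b are not mutually exclusive and can invert, so the division of non-severe events between those two grades is not determined by the text. Total AE counts and SAE status are unaffected. *Severe* also stays separable, on the assumption that *major* and *substantial* mean the same threshold; the text does not say so, and the rewording should make it explicit.

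The attribution gap in D.2.c is real but secondary. It mostly inflates the related class, in the conservative direction, by an amount that the documents do not allow to be computed. No efficacy conclusion is at risk. The finding rests on the protocol text alone, because the DSMP and AE forms could not be checked.

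**What to change.** 1. In D.2.b, define three ordered, non-overlapping grades on one scale, for example none or negligible, some, and substantial interference with usual activities, with one threshold between each neighbouring pair.
2. In D.2.c, add *probably not related* and list the levels in order: definitely not, probably not, possibly, probably, definitely related.
3. Reconcile the use of *related* and *possibly related* in D.2.c.1 and D.2.c.5, so that each reporting rule states which attribution levels it covers.
4. Make the same edits in the DSMP, the AE tracking log and the participant self-report form, since D.2 says the text is copied from the DSMP and C.3.f.13 points the form to D.2.
5. Re-grade the events already logged once, by someone masked to arm, working from descriptions with arm-revealing detail removed where possible. Keep the earlier grade alongside the new one.

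The cost is the rewording of two paragraphs and the reporting rules, matching edits to the DSMP and forms, and one pass over the log. Groups were planned from around October 2015 (C.4.b) and the latest entry in the version history is dated June 2018, so some events will have accumulated. There is one trade-off to accept openly: with a *probably not related* level, some doubtful events may move out of the related class. The sponsor should decide how the reporting rules treat that level before re-grading begins.
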